6.3. Procedures by Visit

6.3.1. Screening

6.3.1.1. Screening Stage 1

Screening Stage 1 visit assessments will be performed between 35 and 1 days prior to Day 1. Initial eligibility assessments will be reviewed and confirmed by the investigator prior to each subject continuing on to the endoscopy with biopsy assessments at Screening Stage 2.

The following procedures will be performed at Screening Stage 1:

- Written informed consent (signed and dated) after the nature of the study has been explained and before any study procedure is performed
- Review of inclusion and exclusion criteria
- Medication and medical history
- Vital signs
 - Heart rate (HR) and systolic and diastolic blood pressure (BP)
 - Respiratory rate

- Body Temperature
- 12-lead ECG
- Physical examination (including fistula exam to determine drainage status if the subject has a fistula) to be conducted according to local practice
- Height and weight
- Chest X-ray (unless one has been performed within 3 months of Screening, documented to be negative, and reviewed by investigator. Subjects who have had a chest X-ray within 3 months prior to Screening will not require a repeat X-ray unless subject is deemed to be at high risk of recent pulmonary infection)
- Blood collection
 - Hematology
 - Serum chemistry
 - FSH (postmenopausal females)
 - Viral hepatitis and human immunodeficiency virus [HIV] serology panel (Refer to Section 6.4.14 for additional details)
 - QuantiFERON®-TB Gold [unless an exam has been done with negative findings within 90 days prior to Screening or subject has a history of latent TB that has been adequately treated within the prior 5 years (Refer to Section 6.4.15 for additional details)] - If the QuantiFERON®-TB Gold result is indeterminate, a repeat QuantiFERON®-TB Gold will be performed.
 - Labs required for Screening Stage 2 can be collected during this visit if the subject happens to be fasting during this visit. Subjects should not be instructed to come in fasting.
- Urine collection
 - Urinalysis
 - Pregnancy test for females of childbearing potential – If urine b-hCG test is positive, confirmation with serum b-hCG test is required
- Fecal collection
 - Fecal infectious studies [C. difficile, other bacteria (including Shigella, Salmonella, Yersinia, E. coli O157, and Campylobacter), and ova and parasite]
- Review concomitant medications
- Adverse event assessment (AEs, SAEs, Adverse Events of Special Interest)
- Electronic diary dispensation (or paper diary if electronic diary is not available) and review of daily diary completion instructions, including symptom monitoring

6.3.1.2. Screening Stage 2

Subjects meeting initial eligibility criteria following completion of the Screening Stage 1 evaluations will return to the clinic for Screening Stage 2 assessments.

Subjects should be instructed to fast from food and non-clear fluids on the evening prior to the visit (which could be Screening Stage 2 visit) to ensure a minimum 8-hour fast prior to the fasted blood sample collection for lipid level measurement.

The following procedures will be performed at Screening Stage 2:

- Review of inclusion and exclusion criteria
- Blood collection (if not collected at Screening Stage 1)
 - Overnight fasting lipid panel
 - [REDACTED]
 - [REDACTED]
- Disease Assessments
 - CDAI Score (must be obtained prior to Screening Stage 2 ileocolonoscopy to assess eligibility criteria; must be performed prior to starting the bowel preparation for the endoscopy; CDAI score ≥ 220 and ≤ 450 is required for continued eligibility)
 - Abdominal Pain and Total Stool Frequency Scores
 - SES-CD Score (to be provided by central reading)
- Ileocolonoscopy and Biopsies (Refer to Section 6.4.18);
- Review concomitant medications
- Adverse event assessment (AEs, SAEs, Adverse Events of Special Interest)
- Review of diary completion, compliance, and symptom monitoring; counsel subject, as needed.

6.3.2. Day 1 (Induction)

Subjects should be instructed to fast from food and non-clear fluids on the evening prior to the Day 1 visit to ensure a minimum 8-hour fast prior to the fasted blood sample collection.

Subjects meeting all eligibility criteria following completion of the Screening Stage 1 and Screening Stage 2 evaluations will return to the clinic for enrollment assessments on Day 1.

Prior to dosing on Day 1, the results of the clinical and laboratory evaluations (as described in Table 1) must be reviewed by the investigator to confirm the continued eligibility of each subject to participate in the study.

The following procedures will be performed on the Day 1 visit:

- Review of inclusion and exclusion criteria
- Review of diary completion and compliance
- Medication and medical history
- Tobacco use status
- Vital signs
 - Heart rate (HR) and systolic and diastolic blood pressure (BP)
 - Respiratory rate
 - Body Temperature
- 12-lead ECG
- Physical examination (including fistula exam to determine drainage status if the subject has a fistula) is to be conducted according to local practice
- Weight
- Blood collection
 - Hematology
 - Serum chemistry
 - Overnight fasting lipid panel
 - [REDACTED]
 - Genetic blood sample (Optional – only collected for subjects who provide genetic testing consent. Refer to Section [6.4.23](#))
 - [REDACTED]
 - [REDACTED]
 - [REDACTED]
 - [REDACTED]
 - [REDACTED]
 - [REDACTED]
- Urine collection
 - Urinalysis
 - Pregnancy test for females of childbearing potential – If urine b-hCG test is positive, the subject does not meet eligibility criteria and cannot proceed with the Day 1 visit. A serum b-hCG would need to be performed and confirmed by central laboratory testing in order to proceed with randomization.

- Fecal collection (may be collected within 72 hours before Day 1 through the end of day on Day 1; however, it is preferable that the stool sample be collected during the first bowel movement in the morning)
 - [REDACTED]
- Disease Assessments
 - CDAI Components
 - Abdominal Pain and Total Stool Frequency Scores
 - [REDACTED]
 - [REDACTED]
- Randomization via RTSM (after all pre-dose procedures have been completed and subject is confirmed to be eligible for the study)
- Subject dosing in clinic (in the morning before eating)
- Review concomitant medications
- Adverse event assessment (AEs, SAEs, Adverse Events of Special Interest)
- Study drug dispensation and review of subject instructions for dosing
- Re-review diary completion instructions, including symptom monitoring and study drug dosing details.

6.3.3. Week 4 (Induction)

Subjects should be instructed to fast from food and non-clear fluids on the evening prior to the Week 4 visit to ensure a minimum 8-hour fast prior to the fasted blood sample collection.

The following procedures will be performed on the Week 4 visit:

- Vital signs
 - Heart rate (HR) and systolic and diastolic blood pressure (BP)
 - Respiratory rate
 - Body Temperature
- Physical examination is to be conducted according to local practice
- Fistula drainage assessment (if applicable) to determine the number of fistula and confirm draining is occurring.
- Weight
- Blood collection
 - Hematology
 - Serum chemistry
 - Overnight fasting lipid panel

- [REDACTED]
- [REDACTED]
- [REDACTED]
- [REDACTED]
- [REDACTED]
- [REDACTED]
- Urine collection
 - Urinalysis
 - Pregnancy test for females of childbearing potential – If urine b-hCG test is positive, confirmation with serum b-hCG test is required
- Disease Assessments
 - CDAI Components
 - Abdominal Pain and Total Stool Frequency Scores
- Perform drug accountability and review subject’s compliance with study drug dosing
- Subject dosing in clinic (in the morning before eating)
- Review concomitant medications
- Adverse event assessment (AEs, SAEs, Adverse Events of Special Interest)
- Study drug dispensation and re-review of subject instructions for dosing
- Review diary completion and compliance; counsel subject as needed

6.3.4. Week 8 (Induction)

Subjects should be instructed to fast from food and non-clear fluids on the evening prior to the Week 8 visit to ensure a minimum 8-hour fast prior to the fasted blood sample collection.

The following procedures will be performed on the Week 8 visit:

- Vital signs
 - Heart rate (HR) and systolic and diastolic blood pressure (BP)
 - Respiratory rate
 - Body Temperature
- Physical examination is to be conducted according to local practice
- Fistula drainage assessment (if applicable) to determine the number of fistula and confirm draining is occurring.
- Weight
- Blood collection

- Hematology
- Serum chemistry
- Overnight fasting lipid panel
- [REDACTED]
- [REDACTED]
- [REDACTED]
- [REDACTED]
- [REDACTED]
- [REDACTED]
- Urine collection
 - Urinalysis
 - Pregnancy test for females of childbearing potential – If urine b-hCG test is positive, confirmation with serum b-hCG test is required
- Disease Assessments
 - CDAI Components
 - Abdominal Pain and Total Stool Frequency Scores
- Perform drug accountability and review subject's compliance with study drug dosing
- Subject dosing in clinic (in the morning before eating)
- Review concomitant medications
- Adverse event assessment (AEs, SAEs, Adverse Events of Special Interest)
- Study drug dispensation and re-review of subject instructions for dosing
- Review diary completion and compliance; counsel subject as needed
- Initiate corticosteroid taper by 2.5 mg per week (Section 6.4.30), for subjects who entered the study on corticosteroids

6.3.5. Week 10 Telephone Call (Induction)

Subjects should be called approximately 14 days to 7 days prior to the Week 12 visit.

The following procedures will be performed at the Week 10 visit:

- Review concomitant medications
- Continue corticosteroid taper by 2.5 mg per week (Section 6.4.30), for subjects who entered the study on corticosteroids (as applicable)
- Adverse event assessment (AEs, SAEs, Adverse Events of Special Interest)

- Review diary completion and compliance; counsel subject as needed and remind of the importance of completion prior to Week 12
- Review schedule of upcoming Week 12 visit. Remind the subject not eat anything prior to the next visit or take study drug on the morning of their next visit. Review bowel preparation activities.

6.3.6. Week 12 (Induction)

Subjects should be instructed to fast from food and non-clear fluids on the evening prior to the Week 12 visit to ensure a minimum 8-hour fast prior to the fasted blood sample collection.

The Week 12 ileocolonoscopy and biopsies should be performed on the same day as the Week 12 visit, preferably in the early morning, to permit morning dosing with study drug. However, if not feasible to perform both the ileocolonoscopy and the clinic visit on the same day, the ileocolonoscopy could be performed anytime within 3 days after the Week 12 clinic visit. If the study activities of this Week 12 visit are to be completed over two different visits, the study drug should be continued until the later of the two visits.

The following procedures will be performed at the Week 12 visit:

- Tobacco use status
- Vital signs
 - Heart rate (HR) and systolic and diastolic blood pressure (BP)
 - Respiratory rate
 - Body Temperature
- 12-lead ECG
- Physical examination is to be conducted according to local practice
- Weight
- Blood collection
 - Hematology
 - Serum chemistry
 - Overnight fasting lipid panel
 - [REDACTED]
 - [REDACTED]
 - [REDACTED]
 - [REDACTED]
 - [REDACTED]
 - [REDACTED]
 - [REDACTED]

- Urine collection
 - Urinalysis
 - Pregnancy test for females of childbearing potential – If urine b-hCG test is positive, confirmation with serum b-hCG test is required
- Fecal collection [may be collected within 3 full days (approximately 72 hours) prior to the visit but must precede the start of a bowel preparation if it is to be collected during the same day as the bowel preparation; however, it is preferable that the stool sample be collected during the first bowel movement in the morning]
 - [REDACTED]
- Ileocolonoscopy and Biopsies (Refer to Section 6.4.18)
- Disease Assessments
 - CDAI Components
 - Abdominal Pain and Total Stool Frequency Scores
 - SES-CD Score
 - [REDACTED]
 - [REDACTED]
- Perform drug accountability and review subject's compliance with study drug dosing
- Subject dosing in clinic (in the morning before eating; last dose of Induction study drug)
- Review concomitant medications
- Continue corticosteroid taper by 2.5 mg per week (Section 6.4.30), for subjects who entered the study on corticosteroids (as applicable)
- Adverse event assessment (AEs, SAEs, Adverse Events of Special Interest)
- Review diary completion and compliance; counsel subject as needed

6.3.7. ATE Day 1

Subjects should be instructed to fast from food and non-clear fluids on the evening prior to the ATE Day1 visit to ensure a minimum 8-hour fast prior to the fasted blood sample collection.

ATE Day 1 may be performed 1 to 7 days following the Week 12 (Induction) visit. However, it must be conducted at least 1 day following the Week 12 ileocolonoscopy and biopsies.

The following procedures will be performed at the ATE Day 1 visit:

- Vital signs
 - Heart rate (HR) and systolic and diastolic blood pressure (BP)
 - Respiratory rate

- Body Temperature
- Blood collection
 - [REDACTED]
 - [REDACTED]
 - [REDACTED]
 - [REDACTED]
 - [REDACTED]
- Urine collection
 - Pregnancy test for females of childbearing potential – If urine b-hCG test is positive, confirmation with serum b-hCG test is required
- Assignment of ATE dose (Refer to [Table 2](#) and [Section 3.3](#))
- Subject dosing in clinic (in the morning before eating)
- Review concomitant medications
- Continue corticosteroid taper by 2.5 mg per week ([Section 6.4.30](#)), for subjects who entered the study on corticosteroids (as applicable)
- Adverse event assessment (AEs, SAEs, Adverse Events of Special Interest)
- Study drug dispensation and re-review of subject instructions for dosing
- Review diary completion and compliance; counsel subject as needed

6.3.8. ATE Week 4

Subjects should be instructed to fast from food and non-clear fluids on the evening prior to the ATE Week 4 visit to ensure a minimum 8-hour fast prior to the fasted blood sample collection.

The following procedures will be performed at the ATE Week 4 visit:

- Vital signs
 - Heart rate (HR) and systolic and diastolic blood pressure (BP)
 - Respiratory rate
 - Body Temperature
- Physical examination is to be conducted according to local practice
- Weight
- Blood collection
 - Hematology
 - Serum chemistry

- Overnight fasting lipid panel
- [REDACTED]
- [REDACTED]
- [REDACTED]
- [REDACTED]
- Urine collections
 - Urinalysis
 - Pregnancy test for females of childbearing potential – If urine b-hCG test is positive, confirmation with serum b-hCG test is required
- Disease Assessments
 - CDAI Components
 - Abdominal Pain and Total Stool Frequency Scores
- Perform drug accountability and review subject’s compliance with study drug dosing
- Subject dosing in clinic (in the morning before eating)
- Review concomitant medications
- Continue corticosteroid taper by 2.5 mg per week (Section 6.4.30), for subjects who entered the study on corticosteroids (as applicable)
- Adverse event assessment (AEs, SAEs, Adverse Events of Special Interest)
- Study drug dispensation and re-review of subject instructions for dosing
- Review diary completion and compliance; counsel subject as needed

6.3.9. ATE Week 8

Subjects should be instructed to fast from food and non-clear fluids on the evening prior to the ATE Week 8 visit to ensure a minimum 8-hour fast prior to the fasted blood sample collection.

The following procedures will be performed at the ATE Week 8 visit:

- Vital signs
 - Heart rate (HR) and systolic and diastolic blood pressure (BP)
 - Respiratory rate
 - Body Temperature
- 12-lead ECG
- Physical examination is to be conducted according to local practice
- Weight

- Blood collection
 - Hematology
 - Serum chemistry
 - Overnight fasting lipid panel
 - [REDACTED]
 - [REDACTED]
 - [REDACTED]
 - [REDACTED]
- Urine collections
 - Urinalysis
 - Pregnancy test for females of childbearing potential – If urine b-hCG test is positive, confirmation with serum b-hCG test is required
- Disease Assessments
 - Abdominal Pain and Total Stool Frequency Scores
- Perform drug accountability and review subject's compliance with study drug dosing
- Subject dosing in clinic (in the morning before eating)
- Review concomitant medications
- Confirm corticosteroid taper by 2.5 mg per week (Section 6.4.30) is complete, for subjects who entered the study on corticosteroids (as applicable)
- Adverse event assessment (AEs, SAEs, Adverse Events of Special Interest)
- Study drug dispensation and re-review of subject instructions for dosing
- Review diary completion and compliance; counsel subject as needed

6.3.10. ATE Week 16

Subjects should be instructed to fast from food and non-clear fluids on the evening prior to the ATE Week 16 visit to ensure a minimum 8-hour fast prior to the fasted blood sample collection.

The following procedures will be performed at the ATE Week 16 visit:

- Vital signs
 - Heart rate (HR) and systolic and diastolic blood pressure (BP)
 - Respiratory rate
 - Body Temperature
- 12-lead ECG

- Physical examination is to be conducted according to local practice
- Weight
- Blood collection
 - Hematology
 - Serum chemistry
 - Overnight fasting lipid panel
 - [REDACTED]
- Urine collections
 - Urinalysis
 - Pregnancy test for females of childbearing potential – If urine b-hCG test is positive, confirmation with serum b-hCG test is required
- Disease Assessments
 - CDAI
 - Abdominal Pain and Total Stool Frequency Scores
 - [REDACTED]
 - [REDACTED]
- Perform drug accountability and review subject's compliance with study drug dosing
- Subject dosing in clinic (in the morning before eating)
- Review concomitant medications
- Adverse event assessment (AEs, SAEs, Adverse Events of Special Interest)
- Study drug dispensation and re-review of subject instructions for dosing
- Review diary completion and compliance; counsel subject as needed

The investigator should consider discontinuation for any subject who has not responded to treatment by ATE Week 16. Subjects who have not shown clinical improvement at ATE Week 16 should complete an Early Study Drug Discontinuation visit and be discontinued from study drug. They will need to return to complete an EOS visit 4 weeks after their last dose.

6.3.11. ATE Week 24

Subjects should be instructed to fast from food and non-clear fluids on the evening prior to the ATE Week 24 visit to ensure a minimum 8-hour fast prior to the fasted blood sample collection.

The following procedures will be performed at the ATE Week 24 visit:

- Tobacco use status
- Vital signs

- Heart rate (HR) and systolic and diastolic blood pressure (BP)
- Respiratory rate
- Body Temperature
- 12-lead ECG
- Physical examination is to be conducted according to local practice
- Fistula drainage assessment (if applicable) to determine the number of fistula and confirm draining is occurring.
- Weight
- Blood collection
 - Hematology
 - Serum chemistry
 - Overnight fasting lipid panel
 - [REDACTED]
 - [REDACTED]
 - [REDACTED]
 - [REDACTED]
- Urine collection
 - Urinalysis
 - Pregnancy test for females of childbearing potential – If urine b-hCG test is positive, confirmation with serum b-hCG test is required
- Fecal collection [may be collected within 3 full days (approximately 72 hours) prior to the visit; however, it is preferable that the stool sample be collected during the first bowel movement in the morning]
 - [REDACTED]
- Disease Assessments
 - CDAI Components
 - Abdominal Pain and Total Stool Frequency Scores
 - [REDACTED]
 - [REDACTED]
- Perform drug accountability and review subject’s compliance with study drug dosing
- Subject dosing in clinic (in the morning before eating)
- Review concomitant medications

- Adverse event assessment (AEs, SAEs, Adverse Events of Special Interest)
- Review diary completion and compliance; counsel subject as needed

6.3.12. ATE Week 36

Subjects should be instructed to fast from food and non-clear fluids on the evening prior to the ATE Week 36 visit to ensure a minimum 8-hour fast prior to the fasted blood sample collection.

The following procedures will be performed at the ATE Week 36 visit:

- Vital signs
 - Heart rate (HR) and systolic and diastolic blood pressure (BP)
 - Respiratory rate
 - Body Temperature
- 12-lead ECG
- Physical examination is to be conducted according to local practice
- Weight
- Blood collection
 - Hematology
 - Serum chemistry
 - Overnight fasting lipid panel
 - [REDACTED]
- Urine collection
 - Urinalysis
 - Pregnancy test for females of childbearing potential – If urine b-hCG test is positive, confirmation with serum b-hCG test is required
- Disease Assessments
 - CDAI Components
 - Abdominal Pain and Total Stool Frequency Scores
- Perform drug accountability and review subject's compliance with study drug dosing
- Subject dosing in clinic (in the morning before eating)
- Review concomitant medications
- Adverse event assessment (AEs, SAEs, Adverse Events of Special Interest)
- Review diary completion and compliance; counsel subject as needed

6.3.13. ATE Week 48

Subjects should be instructed to fast from food and non-clear fluids on the evening prior to the ATE Week 48 visit to ensure a minimum 8-hour fast prior to the fasted blood sample collection.

The following procedures will be performed at the ATE Week 48 visit:

- Tobacco use status
- Vital signs
 - Heart rate (HR) and systolic and diastolic blood pressure (BP)
 - Respiratory rate
 - Body Temperature
- 12-lead ECG
- Physical examination to be conducted according to local practice
- Fistula drainage assessment (if applicable) to determine the number of fistula and confirm draining is occurring.
- Weight
- Blood collection
 - Hematology
 - Serum chemistry
 - Overnight fasting lipid panel
 - [REDACTED]
 - [REDACTED]
- Urine collection
 - Urinalysis
 - Pregnancy test for females of childbearing potential – If urine b-hCG test is positive, confirmation with serum b-hCG test is required
- Fecal collection [may be collected within 3 full days (approximately 72 hours) prior to the visit; however, it is preferable that the stool sample be collected during the first bowel movement in the morning]
 - [REDACTED]
- Disease Assessments
 - CDAI Components
 - Abdominal Pain and Total Stool Frequency Scores
 - [REDACTED]

- [REDACTED]
- Perform drug accountability and review subject's compliance with study drug dosing
- Subject dosing in clinic (in the morning before eating; last dose of ATE study drug)
- Review concomitant medications
- Adverse event assessment (AEs, SAEs, Adverse Events of Special Interest)
- Review diary completion and compliance; counsel subject as needed

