- I. Study drug administration will be in clinic on Day 1, Week 4, Week 8, Week 12, ATE Day 1, ATE Week 4, ATE Week 8, ATE Week 16, ATE Week 24, ATE Week 36, and ATE Week 48 on an empty stomach from the night before after all pre-dose assessments [REDACTED] and procedures have been completed. Subject will take the study drug at home for the rest of the study. The last dose of Induction study drug will be taken at the Week 12 clinic visit. No new study drug will be dispensed between the Week 12 clinic visit and ATE Day 1.
- J. Subjects will be provided with an electronic diary (or paper diary if electronic diary is not available) at the Screening Stage 1 visit and instructed on daily diary completion, including symptom monitoring and study drug dosing details. Diaries of symptoms will be collected daily from the Screening Stage 1 visit through the EOS visit. Study drug dosing details will be entered from Day 1 (Induction) through ATE Week 48 (or the last dose of study drug, if the subject prematurely withdraws from study drug). Diary completion will be monitored for completeness at each return study visit after the electronic diary is dispensed (i.e., Screening Stage 2 through the EOS visit). Subjects will be counseled on missed study drug doses and missed diary entries.
- K. Corticosteroid taper, for those that are on corticosteroid at Screening Stage 1, should be initiated at the Week 8 visit. This taper will continue through ATE, as outlined in Section 6.4.30.
- L. Site personnel to call subjects approximately 2 weeks prior to Week 12 visit for reminder of compliance of diary completion. The site will also review compliance on corticosteroid taper (as applicable), review upcoming schedule for Week 12 and the reminders in preparation for the visit.
- M. AE assessments are to include collection and reporting of AEs, SAEs, and AEs of Special Interest (AESIs). Please refer to protocol Section 7 for further details.
- N. Urine beta human chorionic gonadotropin (b-hCG) testing will be performed before dosing when dosing in-clinic and anytime during all other visits for females of childbearing potential to confirm absence of pregnancy. If urine b-hCG test is positive, confirm with serum b-hCG test.
- O. Required for postmenopausal females.

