5.2. Dosage and Administration

During Induction, subjects will take TD-1473 tablets or placebo once daily for up to 12 weeks. During ATE, subjects will take TD-1473 tablets once daily for up to 48 weeks. For Induction and ATE, subjects will be instructed to take two tablets once daily at approximately the same time each morning before eating and to refrain from eating or drinking anything other than water and non-study medications for at least 30 minutes after dosing.

The Study drug will be taken orally and must be swallowed whole with liquid and not chewed, divided, dissolved, or crushed. If the subject dose is missed in the morning, it can still be taken up to 12 hours after the subject's nominal dosing time, as long as the subject has fasted for at least 4 hours before. After 12 hours post-nominal dosing time, the dose of Study drug should be skipped for that day and the subject should be instructed to take the Study drug on the following day before the first meal of the day.

[REDACTED]

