1. INTRODUCTION

This document describes the plan for the summarization and analysis of clinical data collected in Study 0173 for TD-1473.

[REDACTED]

This document describes the plan for analysis. Once the analyses are in progress, it may become apparent from the data that the planned analyses should be modified. Any substantial modification to the plan will be described in the clinical study report.

Due to the decision to terminate the study early, the exploratory ATE efficacy analyses will not be performed.

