3.7.1.1. Treatment Compliance

Study drug compliance will be calculated as:

$$\frac{100 \times 0.5 \times (\text{number of capsules dispensed} - \text{number of capsules returned})}{(\text{date of last dose} - \text{date of first dose} + 1)}$$

Study drug compliance over the interval from first to last dose in the induction period and the study overall will be summarized as a continuous variable and by rounding to the nearest 0.1% and showing counts and percentages for the following disjoint categories:

- $\geq 120\%$;
- 110% to 120%;
- 90% to 110%;
- 80% to 90%;
- $< 80\%$;

Study drug administration information (date/time and study day) will be provided in a data listing. Study drug accountability information and study drug exposure and compliance will also be provided in data listings.

Study drug discontinuations and reasons for study drug discontinuation will be listed.

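### Overall-study compliance in SAP 3.7.1.1 counts up to 6 planned drug-free days before ATE Day 1 as missed doses, so a fully adherent subject can be reported as low as about 93.5%

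*Protocol*

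**What the plan says.** SAP 3.7.1.1 (Treatment Compliance) takes half the number of units dispensed minus units returned, multiplies by 100, and divides by the date of last dose minus the date of first dose plus 1. The factor of one half matches Protocol 5.2, where "subjects will be instructed to take two tablets once daily". The formula serves two intervals: "Study drug compliance over the interval from first to last dose in the induction period and the study overall will be summarized". Results are shown as a continuous variable and in five categories, with limits at 80%, 90%, 110% and 120%.

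The protocol fixes what happens between the two treatment phases:

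- Section 6.3.6 labels the Week 12 in-clinic dose the "last dose of Induction study drug". Table 1 footnote I says the same and adds: "No new study drug will be dispensed between the Week 12 clinic visit and ATE Day 1".
- Section 6.3.7: "ATE Day 1 may be performed 1 to 7 days following the Week 12 (Induction) visit". Dosing resumes in clinic at that visit.
- Section 5.4 has subjects return all used and unused drug at each visit, so leftover supply is not meant to bridge the interval.
- Section 6.3.6 also says that if the Week 12 activities are spread over two visits, dosing continues to the later visit. The endoscopy may fall up to 3 days after the clinic visit.

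The SAP's own schedule of assessments (Section 1.4, footnotes C, D and I) repeats these rules.

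**The concern.** An interval of 1 to 7 days between two dosing days leaves 0 to 6 days strictly between them. On those days the protocol schedules no dose and supplies no drug. The overall denominator nevertheless contains them, and the numerator cannot. A subject who did exactly what was asked is therefore reported below 100%.

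The error can only run downward. It grows with the gap and shrinks as ATE exposure lengthens, so two equally adherent subjects can receive different figures because of visit scheduling and length of ATE treatment. What is at stake is the accuracy of a descriptive summary and, for some subjects, the category in which they are counted.

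**Working it through.** The documents state no compliance percentage, so there is no planned figure to reproduce. The check applies the SAP formula to a subject who takes every scheduled dose.

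**Inputs**

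- I = Induction doses. A Week 12 visit 84 days after first dose falls on Day 85, giving I = 85. The SAP visit-window table uses Induction Day 84 as nominal, giving I = 84.
- A = ATE doses. The documents give no stop times, so A is an assumption and is varied from 1 to 337 (ATE Week 48).
- g = days from the Week 12 visit to ATE Day 1, 1 to 7 (Protocol 6.3.7). Drug-free days = g - 1.
- Two units per day, so the one-half factor turns units into daily doses.

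**Formula**

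Reported overall compliance = 100 x (I + A) / (I + (g - 1) + A)

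**Full adherence, I = 85**

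| g (drug-free days) | A = 1 | A = 28 | A = 112 | A = 337 |
|---|---|---|---|---|
| 1 (0) | 100.0% | 100.0% | 100.0% | 100.0% |
| 2 (1) | 98.9% | 99.1% | 99.5% | 99.8% |
| 4 (3) | 96.6% | 97.4% | 98.5% | 99.3% |
| 7 (6) | 93.5% | 95.0% | 97.0% | 98.6% |
| 7, split Week 12 visit, 3 extra doses (3) | 96.7% | 97.5% | 98.5% | 99.3% |

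The ends of the g = 7 row are 86/92 = 93.5% and 422/428 = 98.6%. With I = 84 the low end is 85/91 = 93.4%. In the split-visit row the ends are 89/92 and 425/428.

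**Adherence below 100%**

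Let a be the true adherence, so that the reported value is a x (I + A) / (I + (g - 1) + A).

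- a = 95%, 6 drug-free days, A = 14: 0.95 x 99 / 105 = 94.05/105 = 89.6%. The subject is counted in 80% to 90% instead of 90% to 110%.
- a = 95%, 6 drug-free days, general A: 0.95(85 + A) < 0.90(91 + A) gives 0.05A < 1.15, so A < 23 before rounding.
- a = 95%, 5 drug-free days: 0.95(85 + A) < 0.90(90 + A) gives A < 5.
- a = 95%, 4 drug-free days: even at A = 1 the value is 0.95 x 86/90 = 90.8%, so the limit is not crossed.
- a = 95%, 6 drug-free days, ATE Week 48 completer: 0.95 x 422/428 = 93.7%.
- a = 92%, 6 drug-free days, A = 178: 0.92 x 263/269 = 89.9%. Nearer the limit, a much longer ATE exposure can still be misplaced.

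**With the gap removed**

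The denominator becomes I + A, so full adherence gives 100% for every g and every A.

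**The case against.** Several objections carry weight.

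- **Size.** The low figures need the longest interval, and 93.5% also needs a subject who takes exactly one ATE dose. This stands. A reader might infer that any fully adherent ATE subject is reported between 93.5% and 98.6%. The documents do not support that, because the interval may be 1 day, and then nothing is lost.
- **Split visits.** Continued dosing to the later visit shortens the gap. This stands and is shown in the table.
- **Categories.** No fully adherent subject leaves 90% to 110%. A reader might infer that compliant subjects are moved below 90% in general. That is not so: it takes true adherence already below 100%, together with a gap and exposure that combine unfavourably.
- **Early termination.** The SAP Introduction has the phrase "Due to the decision to terminate the study early", and a reader might infer that short ATE exposures, where the error is largest, became more common. The SAP says only that the exploratory ATE efficacy analyses are dropped. It gives no ATE stop times, so that inference is unsupported.
- **A possible rule elsewhere.** In SAP 3.7 a sentence on overall exposure, compliance and adverse event summaries breaks off. Any rule it held cannot be seen. That limits certainty about the whole SAP, but the formula in 3.7.1.1 is complete as printed and has no exclusion.
- **Consequence.** Overall compliance is descriptive, and no visible analysis depends on it. This stands and keeps the point minor.

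A reader might also want the gap removed from overall treatment duration in SAP 3.7.1. That measure is deliberately a calendar span ending at drug return, so changing it would be a preference and not a correction.

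**Conclusion.** The point holds as a minor defect in one formula. As printed, SAP 3.7.1.1 counts 0 to 6 protocol-planned drug-free days as missed doses in overall-study compliance. For a fully adherent subject who enters the ATE, the understatement is between 0 and about 6.5 percentage points; for an ATE Week 48 completer it is at most 1.4 points. Some subjects with true adherence below 100% can be placed one category too low when the gap is long and ATE exposure is short.

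These sizes rest on assumed dose counts (84 or 85 Induction doses, 1 to 337 ATE doses) and assumed adherence levels, because the documents give no distribution of gap length, stop time or adherence. The gap does not enter Induction compliance, and no efficacy analysis that can be read uses the overall figure.

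**What to change.** In SAP 3.7.1.1, define the denominator for the study overall as the sum of two dosing spans for subjects who enter the ATE: (actual last Induction dose date - first dose date + 1) + (last ATE dose date - ATE Day 1 dose date + 1).

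Use the actual last Induction dose date, not the definition in SAP 3.7.1, which sets it to the Week 12 visit dose for everyone who reaches that visit. Under that definition, a subject with a split Week 12 visit could have 3 further doses in the numerator and none in the denominator: with one ATE dose, (85 + 3 + 1)/(85 + 1) = 89/86 = 103.5%, an error in the opposite direction.

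Separately, Table 1 footnote I (last Induction dose at the Week 12 clinic visit) and Protocol 6.3.6 (dosing continued to the later visit when Week 12 is split) must be reconciled; the same pair appears in SAP Section 1.4, footnotes I and C. If the unfinished sentence in SAP 3.7 was meant to carry a rule for overall summaries, complete it.

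The cost of the denominator change is one line of SAP wording and minor programming.
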